## 2. OBJECTIVES AND ENDPOINTS

	Objectives	Endpoints
Primary	To determine the safety and tolerability of fulvestrant, palbociclib and erdafitinib in patients with ER+/HER2-/FGFR-amplified MBC	

Assessment of DLT during the first 4 weeks of treatment (cycle 1)

Determination of MTD

Secondary	

To determine the anti-tumor effect of fulvestrant, palbociclib and erdafitinib in patients with ER+/HER2-/FGFR-amplified MBC

Pharmacokinetic assessments of erdafitinib

	

Progression-free survival (PFS)

Overall response rate (ORR)

Clinical benefit rate (CBR; complete response + partial response + stable disease without disease progression at 6 months)

Pharmacokinetic (PK) assessments of erdafitinib

Correlative	

To determine pharmacodynamic biomarkers of FGFR inhibition

To determine the therapeutic predictive role of FGFR1-4, CCND1-2, CDK4 and CDK6 amplifications, and RB1 and ESR1 mutations on clinical outcome

To determine if the FGFR1 amplification levels by FISH and cfDNA is an early surrogate of response

To determine if the cfDNA results at disease progression show new genomic alterations potentially associated with resistance to CDK4/6 and FGFR inhibition.

	

Serial measurements of serum phosphate, calcium, vitamin D, parathyroid hormone (PTH), FGF23, sFGFR2, sFGFR3 and sFGFR4

FGFR1 FISH

Next Generation Sequencing (NGS) of baseline or archival tumor specimen

Plasma cfDNA at baseline, at 4 weeks and at disease progression

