### 3.6.4 Targeted capture next generation sequencing (NGS)

- Amplification of FGF3/4/19 ligand genes on chromosome 11q12-14 has been observed in 15% of human breast cancers. Notably, one-third of *FGFR1*-amplified tumors also harbor amplification of *CCND1*, *FGF3*, *FGF4* and *FGF19*. This co-amplification has been associated with resistance to estrogen deprivation in ER+ breast cancer and poor patient outcome, thus suggesting the possibility of ligand-receptor cooperativity.
- Recent studies suggest that acquired resistance to CDK4/6 inhibition in ER+ breast cancer results from bypass of cyclin D1-CDK4/6 dependence as a result of *CCNE1* amplification or *RB1* loss.
- *ESR1* mutations, which occur in ~25% of metastatic breast cancer progressing on aromatase inhibitors, are an emerging mechanism of endocrine resistance. The combination of fulvestrant and palbociclib has been shown to be effective against *ESR1*-mutant cell line-derived and patient-derived xenografts. This combination was also effective among patients harboring *ESR1* mutant cancers in the PALOMA-3 trial. Our preliminary data in **Figure 2** would suggest aberrant FGFR signaling limits the effect of fulvestrant/palbociclib and, therefore, in these patients the addition of an FGFR inhibitor may be beneficial.

Therefore, we will determine the therapeutic predictive role of *FGFR1-4*, *FGF3/4/19*, *CCND1-2*, *CDK4* and *CDK6* amplifications, and *RB1* and *ESR1* mutations on clinical outcome. FFPE tissue from primary tumor or from a metastatic tumor biopsy will be collected for NGS in all patients enrolled in the study at the time of registration.

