## 4.2 Exclusion Criteria

- 4.2.1 Prior use of an FGFR inhibitor
- 4.2.2 More than 2 lines of chemotherapy in the metastatic setting. No limit on endocrine therapy lines. Prior exposure to CDK4/6 inhibitor acceptable.
- 4.2.3 Radiation therapy  $\leq 2$  weeks prior to study entry. Patients who have received prior radiotherapy must have recovered from toxicity ( $\leq$  grade 1) induced by this treatment (except for alopecia)
- 4.2.4 Prior cancer therapy (except for endocrine therapy) must have been discontinued for 1 week prior to initiation of study drugs
- 4.2.5 Concurrent anti-cancer therapy other than the ones specified in the protocol is not permitted during study participation. Bisphosphonates or denosumab are allowed
- 4.2.6 Major surgery within 4 weeks of enrollment
- 4.2.7 Herbal preparations are not allowed throughout the study, and should be discontinued 14 days prior to initiation of study treatment
- 4.2.8 Any corneal or retinal abnormality likely to increase the risk of eye toxicity, such as:
  - a. Current corneal pathology such as keratitis, keratoconjunctivitis, keratopathy, corneal abrasion, inflammation or ulceration
  - b. Uncontrolled glaucoma despite standard of care therapy
  - c. Diabetic retinopathy with macular edema
  - d. Known active wet, age-related macular degeneration (AMD)
  - e. Known central serous retinopathy (CSR) or retinal vascular occlusion (RVO)
- 4.2.9 Uncontrolled intercurrent illness including, but not limited to:
  - a. Malabsorption syndrome significantly affecting gastrointestinal function
  - b. Ongoing or active infection requiring antibiotics/ antivirals
  - c. Impairment of lung function (COPD  $>$  grade 2, lung conditions requiring oxygen therapy)
  - d. Symptomatic congestive heart failure (class III or IV of the New York Heart Association classification for heart disease)
  - e. Unstable angina pectoris, angioplasty, stenting, or myocardial infarction within 6 months

- f. Clinically significant cardiac arrhythmia (multifocal premature ventricular contractions, bigeminy, trigeminy, ventricular tachycardia that is symptomatic or requires treatment [National Cancer Institute -Common Terminology Criteria for Adverse Events, Version 4.03, grade 3]
- g. QTcF  $\geq$  480 msec on screening EKG
- h. Known history of clinically significant QT/QTc prolongation or Torsades de Pointes (TdP)
  - i. ST depression or elevation of  $\geq$  1.5 mm in 2 or more leads

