**Notes:**

- Additional tests may be performed at the discretion of the treating investigator as clinically indicated. The sample collection schedules outlined above are based on an ideal subject.
- All appointment/procedures may be performed ± 3 days to accommodate unexpected scheduling issues, weekends and holidays.** The sample schedule should be followed as closely as is realistically possible; however, the schedule may be modified due to problems such as scheduling delays or conflicts (e.g., clinic closure, poor weather conditions, vacations, etc.).
- Shaded cells (gray) represent **RESEARCH** procedures; white cells represent **STANDARD OF CARE** procedures

- Pre-study assessments should be performed within 28 days prior to starting treatment, unless otherwise noted. Please note that the labs obtained on Cycle 1, Day 1 also need to meet eligibility criteria. Screening procedures (i.e. history and physical exam, etc.), excluding labs, which are conducted within 1 week of C1D1 do not need to be repeated. Labs performed on C1D1 for screening are permitted given that they are submitted to the Coordinating Center and approved prior to study treatment initiation.
- Chemistry includes measurement of sodium, potassium, chloride, bicarbonate, BUN, creatinine, glucose, total bilirubin, calcium, total protein, albumin, AST, ALT, and alkaline phosphatase.
- CT scans (chest/abdomen/pelvis) are acceptable for tumor evaluations. MRI of the brain is to be performed only at the discretion of treating physician. Baseline scans should be performed up to 4 weeks prior to study drugs initiation. The scans may be performed ± 5 days of patient's scheduled appointment, to accommodate weekends and holidays
- FFPE blocks may be from the primary tumor (time of original diagnosis) or a metastatic biopsy site. If available, a previously stored fresh-frozen tissue will also be collected. Tissue collected should be submitted at the time of registration. If patients are agreeable, at any time prior, during, or after study drug exposure, an optional (but encouraged) fresh-frozen tissue research biopsy of a metastatic site of disease will be performed and collected (see Section 10.3 for more details). It is assumed that about 20% patients will agree to a fresh biopsy.
- Pill Diary dispensed with study drug for all patients in the study.

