## 10. CORRELATIVE/SPECIAL STUDIES

### 10.1 Overview

Correlate/ Sample	Source	Local/ On-Site Processing	Central Processing	Shipping
FGFR1 testing	FFPE from archival tumor tissue (primary or metastatic)	Submission of FFPE archival tumor tissue block OR Submission of 5 unstained slides cut at 4 microns each placed on charged (plus) slides	Yes ( FGFR1 FISH)	Freq: Same day  Temp: Ambient  Lab: VUMC
Note: Known FGFR amplification by FISH, NGS or cfDNA are acceptable for enrollment if previously done locally				
Next Generation Sequencing (NGS)	FFPE from archival tumor tissue (primary or metastatic)	Submission of FFPE archival tumor tissue OR Submission of: - 1 H&E (or an unstained 4 micron section on a plus [charged] slide) followed by, - 6 serial 20 micron peels placed in a DNase-RNAse free tube (wrapped in parafilm to exclude moisture) followed by, - 1 H&E (or an unstained 4 micron section on a plus [charged] slide) - Peels should be placed in the - 80 freezer upon receipt until extraction is to take place	Yes (DNA extraction for NGS)	Freq: Batched  Temp: Ambient  Lab: VUMC (VUMC will subsequently be responsible to batch ship to MSKCC for NGS analyses)
Whole Blood (NGS control)	Blood- 1 tube, 8 mL, PAXgene or EDTA (purple top)	-Mix by gentle inversion 8 or 10 times - Freeze and store in 20C freezer until ready to ship to MSKCC	Yes	Freq: Batched  Temp: Ambient  Lab: VUMC (VUMC will subsequently be responsible to batch ship to MSKCC for NGS analyses)

**Note:** For patients in which archival tumor is not available and a fresh tumor biopsy is obtained, the main core should be fixed for IHC analysis on site. If additional cores are collected, they can be snap-frozen and submitted as such. The invasive tumor area in the FFPE should be at least 5 mm x 5 mm and contain 20% tumor cellularity.

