## 10.3 Blood Samples for cfDNA

To determine if the *FGFR1* amplification levels is an early surrogate of response, and to determine if the cfDNA results at disease progression show new genomic alterations potentially associated with resistance to CDK4/6 and FGFR inhibition, blood collection for cfDNA will be performed in all patients at: **baseline** (Cycle 1 Day 1), **Day 1 of every even cycle**, and at disease progression (**end-of-treatment**). Initially, the baseline, 4-week and end-of-treatment timepoints will be submitted for cfDNA analysis; the other time points will be stored for future research.

One vial of whole blood should be collected in a Cell-Free DNA BCT tube (Streck tube). Fill the tube completely. Remove the tube from the adapter and immediately mix by gentle inversion 8 to 10 times.

Tubes should be packed according to the **Lab manual** and sent immediately (within 24 h). **Do not freeze or refrigerate specimens collected in Streck tubes as this will compromise measurements of cfDNA.**

If not retrieved on site by VICC CTO personnel, outside sites should ship specimens along with Tissue/Blood Registration Form directly to:

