#### **10.5 Tissue Samples**

To determine the therapeutic predictive role of *FGFR1-4*, *CCND1-2*, *CDK4* and *CDK6* amplifications, and *RB1* and *ESR1* mutations on clinical outcome, FFPE tissue from primary tumor or from a metastatic tumor biopsy will be collected for *FGFR1* FISH analysis and Next Generation Sequencing in all patients enrolled in the study at the time of registration.

Collection of fresh frozen tissue from a metastasis at any point prior, during or after study drugs, is encouraged and desirable, especially in patients that achieve a good clinical response and subsequently have disease progression. The fresh biopsy will follow guidelines as listed in Section 10.4.3.

Summary of required tissue:

A) FFPE block from primary tumor or metastatic tumor biopsy, with adequate tissue to cut the tissue sections described in B) and C) below. Ideally, the invasive tumor area should be at least 5 mm x 5 mm and contain 20% tumor cellularity.

If participating institutions are not allowed to release FFPE blocks, the following should be prepared:

B) To perform *FGFR1* FISH for either pre-screening or central confirmation: 5 unstained slides cut at 4 microns each placed on charged (plus) slides. Do not bake on a hot plate (see 10.3.1).

C) To perform next generation sequencing cut in this order:

1. From a tumor block containing greater than 25 mm^2 of tumor with at least 20% tumor cellularity please provide:
  - a. 1 H&E (or an unstained 4 micron section on a plus [charged] slide) followed by,
  - b. 3 serial 20 micron peels placed in a DNase-RNAse free tube (wrapped in parafilm to exclude moisture) followed by,
  - c. 1 H&E (or an unstained 4 micron section on a plus [charged] slide)
  - d. Peels should be placed in the -80 freezer upon receipt until extraction is to take place.
2. Tumor blocks containing 5-20 mm^2 of tumor with at least 20% tumor cellularity please provide:
  - a) 1 H&E (or an unstained 4 micron section on a plus [charged] slide) followed by,
  - b) 6 serial 20 micron peels placed in a DNase-RNAse free tube (wrapped in parafilm to exclude moisture) followed by,
  - c) 1 H&E (or an unstained 4 micron section on a plus [charged] slide)
  - d) Peels should be placed in the -80 freezer upon receipt until extraction is to take place.

**All formalin-fixed paraffin embedded tissue and/or slides should be sent with a cold pack (except in winter months) to avoid melting that could compromise tissue analysis.**

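### ESR1 and RB1 status for the outcome correlation may be read from a block dating from original diagnosis, so patients altered under later therapy can be called wild-type

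*Combined protocol and SAP*

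**What the plan says.** **Source of the sample.** Section 10.5 ties the predictive analysis of RB1 and ESR1 mutations (with the amplification markers) to tissue: "FFPE tissue from primary tumor or from a metastatic tumor biopsy will be collected for" FISH and sequencing in every patient at registration. Note 4 to the Study Calendar in Section 6 adds that "FFPE blocks may be from the primary tumor (time of original diagnosis) or a metastatic biopsy site". The Section 2 endpoint is "Next Generation Sequencing (NGS) of baseline or archival tumor specimen", and the sequencing row of the Section 10.1 table lists archival FFPE, primary or metastatic. No section limits the age of the block, prefers a metastatic block or asks for the latest one.

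**Biology.** Section 3.6.4 describes ESR1 mutations as an endocrine-resistance mechanism "which occur in ~25% of metastatic breast cancer progressing on aromatase inhibitors". It also says that "acquired resistance to CDK4/6 inhibition in ER+ breast cancer results from bypass of cyclin D1-CDK4/6 dependence", with RB1 loss as one of the two named causes.

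**Population.** Section 4.1.8 requires earlier systemic treatment for metastatic disease. Section 4.2.2 sets no cap on endocrine lines and states: "Prior exposure to CDK4/6 inhibitor acceptable". Section 1, by contrast, describes patients with no earlier CDK4/6 inhibitor.

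**Other samples.** Section 7.1 foresees a baseline metastatic biopsy where feasible. Section 10.5.2 also allows sequencing of snap-frozen metastatic biopsies. Note 4 makes fresh biopsy optional, at any time before, during or after study drug, with uptake assumed at about 20%. Under Section 10.3, plasma is drawn from all patients on Cycle 1 Day 1, and "the baseline, 4-week and end-of-treatment timepoints will be submitted for cfDNA analysis". The purposes given there are FGFR1 amplification level and alterations that newly appear at progression.

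**Analysis.** Section 17 contains no biomarker analysis and no rule on which sample sets a patient's ESR1 or RB1 status.

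**The concern.** A marker that arises under treatment cannot be seen in tissue taken before that treatment. On the protocol's own account, ESR1 mutation and RB1 loss belong to disease that has progressed on an aromatase inhibitor or a CDK4/6 inhibitor. The block that is sequenced may be older than either exposure.

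The resulting error runs in one direction: altered patients join the wild-type group, and none move the other way. Two things follow. The contrast in PFS, CBR or ORR between the groups is diluted, and the altered group, small to begin with, becomes smaller. The extent depends on which block each site happens to send, and the plan does not ask for that to be recorded. A better-timed sample already exists for every patient in the baseline plasma, but no section assigns it to this question.

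**Working it through.** The plan gives no sample size, power or error rate for this correlation, so there is no stated figure to reproduce. The steps below show how large the misclassification could be for ESR1.

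**Inputs from the documents**
- Number of patients N: 26 to 35 (Synopsis).
- ESR1 prevalence p = 0.25 (Section 3.6.4). That figure is for disease progressing on aromatase inhibitors; using it for this trial is an assumption.

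**Assumptions, not in the documents**
- f = share of patients whose only sequenced tissue is a pre-therapy primary; 25%, 50% and 80% are shown, with 100% as the extreme.
- d = share of the mutations already detectable in such a primary; 0, with 20% as a variant.
- No false positives, and full detection in tissue taken after the relevant therapy.

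**Formulas**
- Sensitivity s = 1 − f(1 − d)
- Mutant patients missed = N·p·(1 − s)
- Mutant share of the labelled wild-type group c = p(1 − s) / (1 − p·s)
- Observed difference as a fraction of the true one = 1 − c

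**Worked case, f = 50%, d = 0**
- s = 0.5.
- Expected mutant: 0.25 × 26 = 6.5 and 0.25 × 35 = 8.75.
- Missed: 6.5 × 0.5 = 3.25 and 8.75 × 0.5 = 4.4.
- c = 0.125 / 0.875 = 0.143, so the observed difference is 86% of the true one.

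| f | d | Missed (N=26 / 35) | Identified (N=26 / 35) | c | 1 − c | P(at most 2 identified) (N=26 / 35) |
|---|---|---|---|---|---|---|
| 25% | 0 | 1.6 / 2.2 | 4.9 / 6.6 | 7.7% | 92% | 0.11 / 0.03 |
| 50% | 0 | 3.25 / 4.4 | 3.25 / 4.4 | 14.3% | 86% | 0.35 / 0.17 |
| 80% | 0 | 5.2 / 7.0 | 1.3 / 1.75 | 21.1% | 79% | 0.86 / 0.75 |
| 80% | 20% | 4.2 / 5.6 | 2.3 / 3.2 | 17.6% | 82% | 0.58 / 0.38 |
| 100% | 0 | 6.5 / 8.75 | 0 / 0 | 25% | none to estimate | 1 / 1 |

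The last column is exact binomial with probability p·s per patient. With perfect classification it is 0.026 at N = 26 and 0.003 at N = 35.

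Contamination of the wild-type group cannot exceed 25% here, so dilution alone is moderate. The greater loss is the shrinking of the altered group.

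**Power, for scale.** Take assumed CBRs of 0.30 (mutant) and 0.60 (wild-type), a two-sided 5% level and the normal approximation. Power is 0.25 (N = 26) and 0.33 (N = 35) with perfect classification, 0.12 and 0.15 at f = 50%, and 0.06 and 0.07 at f = 80%, all with d = 0.

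**RB1.** The documents give no prevalence, so no figure can be computed.

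**The case against.** The strongest reply is that the plan is less restrictive than it looks. Sections 7.1 and 10.5.2 admit metastatic biopsies for sequencing, and a block taken after aromatase-inhibitor or CDK4/6-inhibitor therapy would show these alterations. This stands: the error touches only patients whose sole sequenced tissue predates the relevant therapy. It does not dispose of the point, because the baseline biopsy depends on feasibility, fresh biopsy is optional, and fresh tissue obtained during or after study drug does not establish baseline status.

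A second reply concerns plasma. Detecting alterations that are new at progression requires a baseline plasma profile, so baseline cfDNA cannot be confined to FGFR1 level, and nothing forbids using it here. That also stands, but no section assigns it to baseline ESR1 or RB1 status, and the genes covered by the assay are not given.

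Third, the numbers rest on assumptions. Eligibility does not require progression on an aromatase inhibitor, so 25% is not the trial's stated prevalence. The half-and-half block mix is likewise illustrative.

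Fourth, a null result from a small single-arm trial would be weak however status was measured. The power figures bear this out: even perfect classification gives only about 0.25 to 0.33 in the example.

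**Conclusion.** The point holds as a cheap improvement to a correlative objective. The plan permits ESR1 and RB1 status to come from tissue older than the therapy that Section 3.6.4 associates with these changes, and it expresses no preference for better-timed tissue. Under the stated assumptions, with half the patients having only pre-therapy primary tissue, about 3 to 4 of 6.5 to 8.75 ESR1-mutant patients would be missed and about 14% of the labelled wild-type group would be mutant.

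A reader might infer more than the documents support:
- *That altered patients will be analysed as wild-type.* Section 17 has no classification rule, and later metastatic tissue is allowed. The text supports only that they may be.
- *That the protocol calls both changes acquired.* It does so for RB1 loss. For ESR1 it is implied by the link to progression and resistance. The objective names RB1 mutations, while the rationale speaks of loss.
- *That the mutant group will be empty.* This needs every patient to have only a pre-therapy primary block and no such block to carry a mutation.
- *That sample timing is what makes a null result uninterpretable.* It makes matters worse, but size and the single arm already limit the analysis.

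The RB1 part also depends on earlier CDK4/6 inhibitor use, on which Sections 1 and 4.2.2 disagree; the ESR1 part does not. The primary DLT and MTD endpoints are not affected.

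**What to change.** Amend Sections 10.5, 3.6.4 and 2 as follows.

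1. Where more than one block exists, sequence the most recent metastatic one. Record each block's date and site, and its timing relative to earlier endocrine and CDK4/6 inhibitor therapy.
2. Define baseline ESR1 or RB1 status as altered if the alteration is found in the Cycle 1 Day 1 cfDNA, once the assay is confirmed to cover these genes, or in any tissue taken before study treatment. Do not count a patient as wild-type on pre-therapy primary tissue alone; without an informative plasma result or later tissue, the patient is unclassified. Positive findings in older tissue are kept.
3. Report a sensitivity analysis by sample source and timing.
4. Reconcile Sections 1 and 4.2.2 on earlier CDK4/6 inhibitor use.

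The cost is protocol wording, a few data fields and a check of the assay's gene coverage. No visit, draw or biopsy is added, since the baseline plasma is already collected and analysed. Block dates can be entered retrospectively, provided that the status rule is fixed before outcomes are examined. The downside is that plasma can miss alterations in patients who shed little DNA, and some patients may remain unclassified. Power stays low even with correct classification, so the analysis should be presented as descriptive.

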#### 10.5.1 *FGFR1* Fluorescence *In Situ* Hybridization (FISH)

Patients with known (i.e. local determination of) *FGFR1-4* amplification (by NGS, cfDNA or FISH) are eligible for study participation. For patients with *FGFR1* amplification, central confirmation of *FGFR1* amplification by FISH will be performed, but will not be required for study treatment initiation. Patients without known *FGFR1* amplification can send tissue for *FGFR1* amplification screening via FISH analysis at the Vanderbilt-Ingram Cancer Center (VICC) in the CLIA-certified Vanderbilt University Medical Center Cytogenetics Laboratory. Patients with known *FGFR2-4* amplifications (by local determination of NGS, cfDNA or FISH) will not have central confirmation of amplification status by FISH due to their overall low prevalence. From the time tissue arrives at the Coordinating Center Breast Cancer Tissue Core ([name]), a turn-around time of no longer than 7 days should be expected for the FISH results to become available thus determining if a patient is eligible or not.

*FGFR1* FISH will be performed as follows: three to four- $\mu$ m tissue sections will be mounted on sialinized slides and hybridized overnight with the Zytolight SPEC *FGFR1/CEN* 8 Dual Color Probe (ZytoVision, Bremerhaven, Germany). Briefly, after deparaffinization, the slides are denatured in the presence of 10  $\mu$ l probe for 6 min at 73°C and hybridized at 37°C overnight in StatSpin (Thermobrite, Abbott Molecular, Inc.). Post-hybridization SSC washes are performed at 72°C and then the slides are stained with DAPI before analysis. Slides are analyzed with Reflected light fluorescent microscope (Olympus BX60) at 100X for hot spots. Representative images of tumor cells are captured using Cytovision software. Thirty tumor cell nuclei from hot spots or random areas are individually evaluated with the Olympus BX60 at 100X by counting green *FGFR1* and orange centromer 8 (CEN8) signals. The average of *FGFR1* copy number and the *FGFR1/CEN8* is then calculated. Tumors are considered as *FGFR1* positive ('amplified') under one of the following conditions:

- The *FGFR1/CEN8* ratio is  $\geq 2.0$ ;
- The average number of *FGFR1* signals per tumor cell nucleus is  $\geq 6^{40}$ .

